4.2.1.2. Serious Adverse Event (SAE)

An SAE is defined as an AE that:

- Results in death.
- Is life-threatening.
- Requires hospitalization or prolongs existing inpatient hospitalization.
- Results in persistent or significant disability or incapacity.
- Results in a congenital abnormality or birth defect.
- Is an important medical event that requires medical intervention to prevent any of the above outcomes.

4.2.1.3. Other Adverse Events of Special Interest

The following events will be reported as “other adverse events of special interest”:

- Treatment-emergent suicidal ideation or risk, as measured by responses on the C-SSRS on or after first dose of study drug. Suicidal ideation or risk will be defined as a response of “Yes” to either question 4 or question 5 or “Yes” to any suicidal behavior question on the C-SSRS.

Note: Suicidal ideation or risk for suicide prior to randomization (“Yes” to either question 4 or question 5 OR “Yes” to any suicidal behavior question on the C-SSRS) is an exclusion criterion.

- Treatment-emergent moderate to severe depression, as measured by a HADS depression score ≥ 11 on or after first dose of study drug.

Note: Current symptoms of moderate to severe depression prior to randomization (HADS depression score ≥ 11) is an exclusion criterion.

- New pregnancy documented by a positive pregnancy test on or after first dose of study drug.

Note: Pregnancy is an exclusion criterion.

- Treatment-emergent coronavirus disease 2019 (COVID-19) will be selected using the Medical Dictionary for Regulatory Activities (MedDRA) standardized MedDRA query (SMQ) for COVID-19.

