APPENDIX 1. COLUMBIA - SUICIDE SEVERITY RATING SCALE (C-SSRS)

The Columbia Suicide Severity Rating Scale (C-SSRS) provides a standardized method to assess both suicidal ideation and behaviour to identify those at risk for suicide.²¹ The questionnaire must be administered by trained study staff* at Screening and again at the Week 6 (Day 42) and Week 12 (Day 86) study visits. Assessments at Screening will utilize the “Screening” version of the form with ideation to be assessed in the past 3 months and suicidal behaviour within lifetime (the later assessment timing helps to discern if later positive assessments are possibly treatment emergent). Any “Yes” to question 4 or 5 OR “Yes” to any suicidal behaviour question with clear suicidal intent or previous attempt will be considered exclusionary for this study. Assessments at Week 6 (Day 42) and Week 12 (Day 86) study visits will utilize the “Since Last Visit” version of the form with timeframe to be “since last assessment”. Any “Yes” to question 4 or 5 OR “Yes” to any suicidal behaviour question at the Week 6 (Day 42) or Week 12 (Day 86) study visits requires reporting as an AE as well as referral to a qualified Mental Health Professional for follow-up.

*Training by study staff is to be documented via certification in past 1 year on the C-SSRS. Training can be obtained on-line (www.cssrs.columbia.edu/training/training-research-setting).

COLUMBIA-SUICIDE SEVERITY RATING SCALE (C-SSRS)

Screening

Version 1/14/09

Posner, K.; Brent, D.; Lucas, C.; Gould, M.; Stanley, B.; Brown, G.; Fisher, P.; Zelazny, J.; Burke, A.; Oquendo, M.; Mann, J.

Disclaimer:

This scale is intended to be used by individuals who have received training in its administration. The questions contained in the Columbia-Suicide Severity Rating Scale are suggested probes. Ultimately, the determination of the presence of suicidal ideation or behavior depends on the judgment of the individual administering the scale.

Definitions of behavioral suicidal events in this scale are based on those used in The Columbia Suicide History Form, developed by [name] and [name], Conte Center for the Neuroscience of Mental Disorders (CCNMD), New York State Psychiatric Institute, [name]. (Oquendo M. A., Halberstam B. & Mann J. J., Risk factors for suicidal behavior: utility and limitations of research instruments. In M.B. First [Ed.] Standardized Evaluation in Clinical Practice, pp. 103 -130, 2003.)

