The QSU-Brief is a 10-item questionnaire that will be administered Day 0, and at various visits during the treatment period (Day 2, Week 1 through Week 6). Item scores will be assigned using the scoring key pre-printed on the questionnaire (see Appendix 4 of the study protocol). A total QSU-Brief score will be derived for each subject, providing all questions have been answered.

Minnesota Withdrawal Scale (MNWS)

The MNWS is a 9-item questionnaire that will be administered at Day 0, and at various visits during the treatment period (Week 1 through Week 7). Item scores will be assigned using the scoring key pre-printed on the questionnaire (see Appendix 5 of the study protocol). A total MNWS score will be derived for each subject, providing all questions have been answered.

Columbia Suicide Severity Rating Scale (C-SSRS)

The C-SSRS (see Appendix 1 of the study protocol) is an assessment of both suicidal ideation and behavior. Suicidal ideation or risk for suicide (“Yes” to either question 4 or question 5 OR “Yes” to any suicidal behavior question on the C-SSRS) is an exclusion criterion.

The “Screening” version of the C-SSRS assesses suicidal ideation over the past 3 months, and suicidal behavior over the subject’s lifetime. The “Screening” version of the C-SSRS will be administered at SV1. The “Since Last Visit” version of the C-SSRS evaluates both suicidal ideation and behavior since the last assessment. This version of the C-SSRS will be administered at Week 6 and Week 12.

C-SSRS Suicidal Ideation: In both the “Screening” and “Since Last Visit” forms, there are 5 items that assess suicidal ideation. Subjects indicate (Yes/No) whether each of the following applies:

1. Wish to be dead
2. Non-specific active suicidal thoughts
3. Active suicidal ideation with any methods, without intent to act
4. Active suicidal ideation with some intent to act, without specific plan

5. Active suicidal ideation with specific plan and intent.

Each item will be assigned a numeric score (0=No, 1=Yes).

C-SSRS Suicidal Behavior: In both the “Screening” and “Since Last Visit” forms, there are 5 items that assess suicidal behavior. Subjects indicate (Yes/No) whether each of the following applies:

1. Actual attempt (non-fatal)
2. Interrupted attempt
3. Aborted attempt
4. Preparatory acts or behavior
5. Suicidal behavior

Each item will be assigned a numeric score (0=No, 1=Yes).

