10.2.11. Questionnaires

The HADS, QSU-Brief, and MNWS questionnaires will be administered at baseline and after the start of treatment. Scores for each questionnaire will be derived as described in Section 8.6.

Questionnaire scores will be summarized using descriptive statistics. For each score, the actual value, change from baseline and percent change from baseline will be summarized by treatment arm and visit. Only subjects with non-missing results at both the baseline and post-baseline visit will be summarized at each time point.

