11.1.2. Other Adverse Events of Special Interest

Other adverse events of special interest were defined in Section 4.2.1.3 as the following events:

- treatment-emergent suicidal ideation or behavior
- treatment-emergent moderate to severe depression
- new pregnancy
- COVID-19

The number (%) of subjects with each event will be summarized by treatment arm.

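### The suicidal ideation row in the SAP counts only C-SSRS items 4-5 or behavior, and ideation items 1-3 enter no planned summary

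*SAP*

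**What the plan says.** SAP 2.1 names the C-SSRS among the safety assessments. SAP 6.4.2 says of both versions of the form that "there are 5 items that assess suicidal ideation", and adds "Each item will be assigned a numeric score (0=No, 1=Yes". The Screening version is given at the first screening visit and the Since Last Visit version at Weeks 6 and 12. Item 3 on the SAP's own list reads "Active suicidal ideation with any methods, without intent to act".

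SAP 4.2.1.3 defines the suicidality event of special interest: "Suicidal ideation or risk will be defined as a response of “Yes” to either question 4 or question 5", or any behavior item. SAP 11.1.2 lists the event as "treatment-emergent suicidal ideation or behavior" and plans one output: "The number (%) of subjects with each event will be summarized by treatment arm".

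Protocol Appendix 1 uses the same threshold for compulsory reporting. At Week 6 or Week 12, a positive answer to item 4, item 5 or a behavior item "requires reporting as an AE as well as referral to a qualified Mental Health Professional for follow-up".

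**The concern.** The label names ideation without qualification, but the rule leaves out three of the five ideation levels. A subject who newly endorses item 3, which the SAP itself words as active suicidal ideation, is not counted. Nothing else in the planned tables fills the gap.

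The HADS event beside it is handled differently. Its label, moderate to severe depression, matches its cut-off, and SAP 10.2.11 also summarizes the HADS scores by arm and visit. The C-SSRS has neither a matching label nor a fuller summary.

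Safety objective 1 (SAP 3.4) is to evaluate the safety profile of cytisinicline against placebo. The protocol excludes subjects at current risk, repeats the C-SSRS on treatment, and in Section 1.3 cites mental-health warnings for varenicline, which was developed partly from cytisine. The same section also reports a trial of 8,144 participants with no significant increase in neuropsychiatric events attributable to varenicline. No raised risk is assumed here. The issue is whether the tables could describe ideation by arm if it occurred.

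**Working it through.** The plan states no figure to reproduce, so the main check follows items 1-3 through each place where a summary could use them.

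- **Safety endpoints (SAP 4.2):** adverse events, laboratory, vital signs, ECG, concomitant medications. The C-SSRS is not listed.
- **Baseline questionnaires (SAP 8.6):** FTND, HADS, SEQ-12, QSU-Brief, MNWS. No C-SSRS.
- **Subject-reported outcomes (SAP 10.2.10):** grouped by efficacy success or failure; the C-SSRS is not named.
- **Post-baseline questionnaires (SAP 10.2.11):** "The HADS, QSU-Brief, and MNWS questionnaires will be administered at baseline and after the start of treatment". No C-SSRS.
- **By-visit safety tables (SAP 11):** laboratory, vital signs, weight, ECG. No C-SSRS.
- **Event of special interest (SAP 4.2.1.3, 11.1.2):** items 4-5 or behavior only.
- **Adverse-event tables (SAP 11.1):** items 1-3 enter only if an investigator records an event, because Appendix 1 makes reporting compulsory only for items 4-5 or behavior.
- **Listings (SAP 6.2):** data are generally listed, so items 1-3 can appear there, subject by subject.

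The starting level is also untabulated. Exclusion 10 (Protocol 8.2) covers items 4-5, and behavior with clear intent or a previous attempt. It does not bar a subject positive only on items 1-3.

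**Response patterns missed.** With no behavior item positive, five yes/no items give 2^5 - 1 = 31 non-zero patterns. Those confined to items 1-3 number 2^3 - 1 = 7. The form asks items 3-5 only if item 2 is positive. Under that rule there are 2 × (1 + 8) - 1 = 17 non-zero patterns, of which 2 × (1 + 2) - 1 = 5 are confined to items 1-3. These count patterns, not expected frequencies.

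**Illustration of size.** The arm size of 250 is from the plan, and the output is by arm. Two inputs are assumptions: r, the share of an arm with any new ideation, and q, the share of those reaching item 4 or 5. Behavior items are ignored.

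- Subjects with any ideation: 250 × r. At r = 0.02 this is 5.
- Expected in the row: 250 × r × q. At r = 0.02 this is 0.5 for q = 0.10 and 1.25 for q = 0.25.
- Probability that the row shows zero: (1 - r × q)^250.
  - q = 0.10: (1 - 0.002)^250 = 0.61.
  - q = 0.25: (1 - 0.005)^250 = 0.29.
- Wider range: r = 0.01, q = 0.10 gives 0.999^250 = 0.78. With r = 0.04, q = 0.50 it is 0.98^250 = 0.006.

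The zero probability depends heavily on the assumed rates. The omission of items 1-3 does not depend on them.

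**The case against.** The threshold looks deliberate. It is prespecified, printed in full in SAP 4.2.1.3 and identical to the compulsory reporting rule in Appendix 1. On behavior it is broader than exclusion 10 in the protocol, which is limited to clear intent or a previous attempt. All of this stands: there is no conflict with the protocol, and the rule should stay.

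A reader might infer that the SAP declares subjects with only items 1-3 free of ideation. It does not. They are simply not counted in that event.

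A reader might also infer that adverse-event coding can never capture these answers. Appendix 1 sets a minimum, not a ceiling. Protocol 14 and 14.1 count events reported by or elicited from the subject and define an adverse event broadly, so an investigator may record new ideation below the threshold. Capture would then be discretionary and possibly uneven, which is not a complete summary.

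Mood is followed elsewhere through the HADS and MNWS, but neither measures ideation. SAP 11 plans no statistical comparison for any safety endpoint, so what is lost is descriptive. The data are collected, scored and generally listed, so the gap can be closed without new collection.

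One caution applies to the remedy. Screening ideation covers the past 3 months, while later visits cover the time since the last assessment. For Week 6 that reaches back to screening, up to 28 days before randomization: 42 + 28 = 70 days at most, ignoring the visit window. A rise above the screening category is therefore not a clean measure of emergence on treatment.

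**Conclusion.** The point holds as a gap in safety reporting. The only C-SSRS row carries a label wider than its rule, and three of the five ideation items have no planned summary at baseline or on treatment. A low or zero count could be misread as little or no ideation of any kind, although the SAP makes no such statement.

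Efficacy inference, alpha, sample size and subject-protection rules are unaffected. The conclusion rests on the text alone. The illustrative 61% to 29% chance of an empty row in one arm rests on assumed rates (2% with any ideation, 10% to 25% of those reaching items 4-5) and ignores behavior items.

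**What to change.** 1. In SAP 4.2.1.3 and 11.1.2, keep the present rule as its own row and rename it to match, for example *ideation with intent (items 4-5) or suicidal behavior*.
2. In SAP 11.1.2, add one descriptive table by arm at screening, Week 6, Week 12 and any post-baseline assessment. Give n (%) for each ideation item 1-5, any ideation, highest ideation category, each behavior item and any behavior.
3. Show both any post-baseline ideation and the shift from the screening category. Footnote the different recall periods and state that the shift is descriptive.

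No referral, adverse-event reporting or eligibility rule changes. The cost is one extra table from items already scored, plus a wording change in two sections. A few more low-level positives may be shown in every arm, including placebo.

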4.2.1.4. End of Treatment (EOT) Visit

As specified in the protocol, post-treatment assessments will be done for all subjects approximately 1 – 3 days after the last dose of study drug (the EOT assessments).

The timing of EOT assessments will be different for subjects who complete treatment and subjects who discontinue treatment early. Subjects that complete treatment will have EOT assessments done at the Week 12 (Day 86/EOT) visit. Subjects who discontinue treatment early, will have EOT assessments done at an earlier visit that coincides with their date of treatment discontinuation. The visit at which EOT safety assessments were done will be documented in study datasets.

Subjects who discontinue treatment early are expected to continue in the study through Week 24. Therefore, it is expected that the procedures outlined under the Week 12 (Day 86/EOT) visit will be repeated at that time.

In order to accurately summarize changes from baseline to EOT in safety endpoints, the EOT safety assessments for all subjects will be combined into a derived visit named “EOT”. That visit will be included in summary tables of safety endpoints.

4.3. Pharmacokinetic and Pharmacodynamic Evaluations

None planned.

5. TRIAL CONDUCT CONSIDERATIONS

5.1. Changes in Inclusion and Exclusion Criteria

No changes are planned.

5.2. Interim Analysis and Early Stopping

None planned.

5.3. Sample Size Adjustment

If higher than expected early treatment discontinuations (>5%) occur before completion of 6 weeks study treatment due to reasons other than adverse events, additional enrollment may be allowed up to 10% or 75 subjects.

6. DATA ANALYSIS CONSIDERATIONS

6.1. Clinical Databases

There will be two clinical data sources for this study: a web-based interactive response technology (IRT) application and an eCRF database.

IRT will be used to collect subject diary data, randomize subjects, and allocate study drug. In general, data collected in the IRT application will be transferred to the eCRF database. The

following data will not be transferred to the eCRFs but will be extracted from the IRT application after the eCRF database is locked:

- Subject randomization data: date randomized, value of stratification factor at randomization, treatment arm assignment.
- Subject treatment-diary data: date and time of each dose (or indication if dose was missed) as recorded by subjects each day during the treatment period.

All other subject data will be entered into the eCRF database and will be extracted from that application after the eCRF database is locked.

6.2. General Considerations

Statistical analyses will be performed at the end of the study after the last subject has completed the Week 24 visit, all data have been reported, cleaned, and the eCRF database has been locked.

Medical history events and adverse events will be coded to standard “preferred terms” and “system organ classifications (SOC)” using the Medical Dictionary for Regulatory Activities (MedDRA) Version 23.1 or higher. Concomitant medications will be coded using the World Health Organization Drug Dictionary (WHODrug) Version Mar-2021 B2 or higher.

All statistical programming will be done using SAS® Version 9.4 or higher (SAS® Institute, Cary, North Carolina). All tables, figures and listings will be produced in landscape format.

In general, all data will be listed by treatment arm, subject and visit/time point where appropriate. The summary tables will have columns corresponding to, or be stratified by, treatment arm. In listings and summary tables the treatment arms will be ordered and labelled as follows: Placebo, Cytisinicline 6 Weeks, Cytisinicline 12 Weeks.

The total number of subjects under the stated analysis set in each treatment arm (N) will be displayed in the header of summary tables.

Data will be summarized using descriptive statistics for continuous variables. Unless otherwise specified, descriptive statistics will include number of subjects (n), mean, standard deviation, minimum, median and maximum. In case of $n < 2$, where n indicates the number of subjects with evaluable data at the particular time point, the standard deviation will be empty. The statistic “Missing” will also be presented as the number of missing entries/subjects, if any at that visit/timepoint, and presented as a summary statistic only when non-zero. The minimum and maximum statistics will be presented to the same number of decimal places as the original data. The mean and median will be presented to one more decimal place than the original data, whereas the standard deviation will be presented to two more decimal places than the original data.

In summary tables of categorical variables, counts and percentages will be used. The count [n] indicates the actual number of subjects with a particular value of a variable or event, which should always be less than or equal to the total number of subjects with non-missing value of the variable or event [M]. Percentage will be obtained by: $\% = (n/M) \times 100$. Unless otherwise stated, all percentages will be expressed to one decimal place.

In by-visit summary tables only scheduled visits/timepoints will be summarized. In listings all visits and timepoints with any data collected, including both scheduled and unscheduled ones, will be included.

All dates in tables, figures and listings will be displayed in YYYY-MM-DD format.

All outputs will be sent to Achieve as electronic files in RTF format documents. In addition, RTFs for similar outputs (eg, tables, figures, listings) will be concatenated, output to bookmarked PDF files, and sent to Achieve.

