14. SAFETY ASSESSMENTS

All subjects will be monitored for adverse events starting at screening (pre-existing), by telephone contact on Day 1, at clinic visit on Day 7, then weekly throughout the Treatment Period (Weeks 2 through 12) and monthly during the Follow-up Period (see [Table 4](#) and [Table 5](#)). 12-lead ECG evaluations will be obtained on Week 6 and Week 12. Laboratory (hematology and chemistry) evaluations will be performed at the Week 1, Week 6, and Week 12 clinic visits using a central laboratory.

Safety will be assessed by consideration of all adverse events reported by or elicited from the subject and clinically significant abnormalities detected on 12-lead ECG or hematology and serum chemistry tests. Worsening of other preexisting medical conditions and any changes to concomitant medications/treatments will also be taken into account in this evaluation.

In addition to the planned times, safety procedures can be performed at any time when considered necessary by the Principal Investigator or attending Research Physician.

In the event of any clinically significant abnormalities identified by the investigating physician, subjects will be followed until:

- It has resolved/returned to normal or baseline.
- The event has stabilized at a level acceptable to the Investigator and is not considered to be clinically significant.
- It has been shown to be chronic during follow-up assessment.

All adverse events (serious and non-serious) beginning at randomization (prior to dosing) through the Week 24 visit will be recorded in the subject's CRF.

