11.2. Hematology and Chemistry Data

Hematology and chemistry samples will be collected at SV1, Week 1, Week 6, and at Week 12 (Day 86/EOT).

The protocol-specified hematology tests are hemoglobin, red blood cells (erythrocytes), platelets, white blood cells (leukocytes), and absolute counts for neutrophils, lymphocytes, monocytes, eosinophils and basophils. The protocol-specified serum chemistry tests are total protein, albumin, total bilirubin, alanine aminotransferase (ALT), aspartate aminotransferase (AST), alkaline phosphatase, glucose, sodium, potassium, calcium, creatinine, creatinine clearance/glomerular filtration rate and blood urea nitrogen (BUN). Samples will be analyzed by a central laboratory. If the central laboratory does not provide results in Système International (SI) units then the designated Clinical Research Organization (CRO) will convert all laboratory results to SI units prior to analysis. The SI unit values will be derived from CDISC controlled terminology.

Hematology and serum chemistry values may be reported by the central laboratory as less than the lower limit of quantitation (eg, result reported as “<10 ng/mL”) or greater than the upper limit of quantitation (eg, result reported as “>2000 ng/mL”). Results reported as “<X” will be converted to a numeric result of “X” prior to statistical analysis (eg, <10 ng/mL will be converted to 10 ng/mL). Results reported as “>X” will be converted to a numeric result of “X” prior to statistical analysis (eg, >2000 ng/mL will be converted to 2000 ng/mL). Values outside the upper and lower limits of quantitation will be presented as collected (eg “<10 ng/mL”) in the corresponding listings.

The following laboratory summaries will be provided for the protocol-specified tests by treatment arm and visit:

- Actual value and change from baseline will be summarized using descriptive statistics, by laboratory test and visit.
- Shift tables will be used to summarize the number (%) of subjects with changes from baseline in normal range flag (L=low, N=within normal limits, H=high), by laboratory test and visit.

Separate summary tables will be produced for serum chemistry tests and hematology tests. In addition to summary tables, separate listings of protocol-specified laboratory test results will be produced.

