11.3. Vital Signs and Weight

Vital signs, including weight, will be assessed at SV1, Day 0 (Randomization), and at each clinic visit during the treatment period.

For each test (oral temperature, pulse rate, systolic and diastolic blood pressure, weight), the actual value and change from baseline will be summarized by treatment arm and visit using descriptive statistics. For change from baseline, only subjects with non-missing results at both the baseline and post-baseline visit will be summarized at each time point.

Shift table by treatment group will summarize the number (%) of subjects who gain or loss $\geq 5\%$ of their baseline body weight at each visit, as well as subjects who gain or loss $\geq 10\%$ of their baseline body weight at each visit.

The number and percentages of subjects reporting potentially clinically significant (PCS) vital signs at any time post-baseline will be summarized by treatment arm, where PCS will be defined as follows:

	PCS – Low if:			PCS – High if:		
	Observed Value is:	AND	Decrease from Baseline is:	Observed Value is:	AND	Increase from Baseline is:
Systolic Blood Pressure	<85 mmHg		≥ 20 mmHg	>160 mmHg		≥ 20 mmHg
Diastolic Blood Pressure	<40 mmHg		≥ 10 mmHg	>90 mmHg		≥ 10 mmHg
Heart Rate	<35 bpm		≥ 15 bpm	>100 bpm		≥ 15 bpm

11.4. 12-Lead ECG Interpretation

A 12-lead ECG will be done at the SV1, Week 6 and Week 12 (Day 86/EOT) visits.

An overall interpretation (normal, abnormal – not clinically significant, abnormal – clinically significant) will be recorded in the CRF for each assessment.

The number (%) of subjects with shifts in overall interpretation (eg, normal to abnormal – NCS, normal to abnormal - CS) will be summarized by visit and treatment arm. The number (%) of subjects with at least one shift from a baseline result of “normal” or “abnormal – not clinically significant” to a post-treatment result of “abnormal – clinically significant” will also be reported.

In addition, an ECG listing will be provided.

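### Post-baseline laboratory values from unscheduled visits enter no laboratory summary table, and no table counts subjects by size of abnormality or by worst value at any time after first dose

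*SAP*

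**What the plan says.** SAP 6.2 sets the general rule for tables: "In by-visit summary tables only scheduled visits/timepoints will be summarized". For listings it says: "In listings all visits and timepoints with any data collected, including both scheduled and unscheduled ones, will be included".

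SAP 11.2 schedules hematology and chemistry at SV1, Week 1, Week 6 and Week 12, and plans two kinds of summary:

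- Continuous: "Actual value and change from baseline will be summarized using descriptive statistics, by laboratory test and visit". Under SAP 6.2 the default "descriptive statistics will include number of subjects (n), mean, standard deviation, minimum, median and maximum".
- Categorical: "Shift tables will be used to summarize the number (%) of subjects with changes from baseline in normal range flag", with three classes (low, normal, high), again by test and visit.

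SAP 11 and 4.2.1.4 add one derived visit, EOT, to the by-visit safety tables. It brings in the end-of-treatment assessments of subjects who stop treatment early.

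Protocol 14 allows tests off schedule: "safety procedures can be performed at any time when considered necessary by the Principal Investigator or attending Research Physician". It also requires clinically significant abnormalities to be followed until they resolve, stabilise or prove chronic. Protocol Table 5 has no safety laboratory tests after Week 12, so a retest in follow-up is off schedule.

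For vital signs, SAP 11.3 plans that subjects with "potentially clinically significant (PCS) vital signs at any time post-baseline will be summarized by treatment arm". For ECG, SAP 11.4 counts subjects with at least one shift to a clinically significant abnormal reading.

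**The concern.** An unscheduled blood draw is often made to recheck an abnormal result or to investigate a symptom. Under the SAP 6.2 rule, the result of such a draw after baseline has no place in the laboratory tables. If a Week 1 value is raised and a retest ten days later is higher, the tables show the Week 1 value and not the peak.

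The second gap is in grading. The one laboratory table that counts subjects puts a value just above the limit and a value many times the limit into the same class.

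SAP 11 plans no statistical tests between arms for safety, so these descriptive tables are the arm comparison. A reader who wants to know how many subjects per arm ever had a marked laboratory change would have to count them from listings.

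**Working it through.** The plan states no figure on this point, so there is none to reproduce. The check follows a post-baseline laboratory value through each planned output, then uses two illustrations on stated assumptions.

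**Where a post-baseline value goes**

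| Output | Unscheduled value included? | Counts subjects? | Shows size? |
|---|---|---|---|
| Continuous table, SAP 11.2 | No (by visit) | No | Yes, through mean, SD, minimum, maximum |
| Low/normal/high shift, SAP 11.2 | No (by visit) | Yes | No |
| Adverse event tables, SAP 11.1 | Yes, if judged clinically significant (Protocol 14.3.1) | Yes | Not by laboratory value |
| Listings, SAP 6.2 | Yes | No | Yes |

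No row of this table has yes in all three columns.

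The adverse event row needs a closer look. Protocol 14.3.1 leaves clinical significance to the investigator and gives no numeric criterion. Protocol Table 6 grades severity by interference with activity and need for medical intervention. A large enzyme rise without symptoms can therefore be graded mild.

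**Illustration 1: what the two laboratory tables can separate.** Assume 250 subjects, an ALT upper limit of 40, 249 simulated values within normal limits, and one further value.

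| Extra value | High count | Mean | SD | Median | Maximum |
|---|---|---|---|---|---|
| 44 | 1 | 21.5 | 5.70 | 21.6 | 44 |
| 400 | 1 | 22.9 | 24.57 | 21.6 | 400 |

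The shift table cannot tell these apart; the continuous table can.

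Now assume ten high values in each of two cases. In case 1, one is 400 and nine are 44. In case 2, one is 400 and nine are 85.

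- High count: 10 in both.
- Maximum: 400 in both.
- Difference in mean: 9 x (85 - 44) / 250 = 369 / 250 = 1.5.
- Subjects above 2 x 40 = 80: one in case 1, ten in case 2.

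The mean and SD move, but neither planned table gives the count of one against ten.

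**Illustration 2: how often a scheduled draw sees a transient change.** Scheduled post-baseline draws fall on Days 7, 42 and 86, so the gaps are 42 - 7 = 35 days and 86 - 42 = 44 days. Assume onset is equally likely on each of Days 1 to 84. An abnormality lasting d days overlaps a draw on day v if its onset lies between v - d + 1 and v.

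| Duration | Onset days that overlap a draw | Seen | Missed by every scheduled draw |
|---|---|---|---|
| 7 days | 7 + 7 + 5 = 19 of 84 | 23% | 77% |
| 14 days | 7 + 14 + 12 = 33 of 84 | 39% | 61% |
| 28 days | 7 + 28 + 26 = 61 of 84 | 73% | 27% |

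This describes the visit schedule, not a loss caused by SAP 6.2. It shows only that a short-lived change would often be seen, if at all, through an extra draw. If no extra sample is taken, no table can recover it.

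**The case against.** The case against is substantial, and several stronger readings fail on it.

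- **That all laboratory summaries are graded, so mild and marked rises look alike.** One of the two is continuous and reports minimum and maximum. Only the shift table merges mild and marked rises.
- **That unscheduled values never reach a summary table, or are all lost.** Those judged clinically significant become adverse events and are tabulated by preferred term and severity, whatever the visit. SAP 6.3 lets an unscheduled pre-dose value serve as baseline. The derived EOT visit covers early stoppers. Everything is listed.
- **That the most abnormal values are the ones most likely to be missing.** The documents do not show this. Where a scheduled draw prompts the retest, the prompting value is already in the tables.
- **That the gaps of 35 and 44 days come from the SAP rule.** They come from the protocol visit schedule.
- **That the vital signs table certainly includes unscheduled readings.** SAP 11.3 refers to any time post-baseline but does not say so expressly. The same holds for ECG in SAP 11.4.

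It can also be said that safety is reviewed during the trial by the DSMC, that no safety inference is tested, and that no section makes the entry limits on-study thresholds. All of that is true.

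What remains is narrow. The adverse event route depends on judgement and does not grade by laboratory size. The maximum is one number per test, visit and arm, from scheduled draws. Neither replaces a count of subjects. Even if the vital signs and ECG tables used scheduled readings only, they would still count subjects across visits, which no laboratory table does.

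**Conclusion.** The gap is real but limited to display. After baseline, unscheduled laboratory values enter no SAP 11.2 table, and no table counts subjects by size of abnormality or by worst value at any time after first dose. This follows from reading SAP 6.2 together with 11.2 and needs no numerical assumption.

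Its size in subjects is unknown, because the documents give no expected number of unscheduled draws or of marked abnormalities. The percentages in the working rest on an assumed uniform onset and assumed durations, and they measure the schedule rather than the SAP rule. The ALT values are illustrative.

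A reader might infer that a laboratory signal would be hidden. The documents do not support that, given the continuous table, the adverse event tables and the listings. They support a smaller statement: the arm comparison of laboratory safety lacks the subject counts that the same SAP provides for vital signs and ECG. Efficacy, type I error and sample size are unaffected. It is worth changing because the change is cheap.

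**What to change.** Add two tables to SAP 11.2, both by arm on the Safety Set.

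1. A shift from baseline to worst post-baseline value for each test, including unscheduled results and stated to be exempt from the scheduled-visit restriction in SAP 6.2. For tests that can be abnormal in either direction, show worst low and worst high separately.
2. The number and percentage of subjects who newly cross a prespecified threshold at any time after first dose. The trial's own entry limits would serve: ALT or AST >2.0 x ULN, and creatinine clearance <60 mL/min. Subjects beyond these limits are excluded at entry, so apart from eligibility deviations a crossing is new. The SAP should say that they are reporting categories only and not management rules.

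A footnote giving the number of subjects per arm with at least one unscheduled draw would help. More draws mean more chances to be counted as abnormal, and testing may differ between arms.

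The cost is two tables from data that must already be listed; creatinine clearance is already among the SAP 11.2 tests. The downside is slightly higher ever-abnormal counts in all arms.
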